After completing the 10-day CGM session, the sensor will be removed by a trained study staff member. To remove the sensor, the adhesive patch will be gently peeled off from the skin. Removal of the sensor is a painless procedure. The sensor/transmitter will be discarded after use. CGM removal will occur during Visit 3.

Hyperinsulinemic-euglycemic clamp (Visit 3): After an overnight fast, eligible subjects will return to the YNHH HRU. Two IV catheters will be inserted: one into a distal arm or hand vein that will be placed in a heated box to allow for the sampling of arterialized venous blood; the second into an antecubital vein for administration of a primed (200 mg/m^2) and continuous infusion of [6,6-2H] Glucose and [2H5] Glycerol

(non-radioactive stable isotopes) as well as for collecting blood samples for insulin and glucose measurements. After an equilibration period lasting 2 hours., the 2-step euglycemic-hyperinsulinemic clamp study will be performed. A primed-continuous infusion of regular insulin will be given at 8 mU/(m^2 × min) during the first 2 hours, and increased to 40 mU/(m^2 × min) for the subsequent 2 hours. Plasma glucose levels will be measured every 5 min, and a variable glucose infusion will be initiated to maintain levels at ~90 mg/dl. Plasma samples will be drawn at baseline and throughout the infusion period for measurement of isotope enrichment, insulin, NEFA, glycerol turnover, and additional hormones which may be altered with lactation. Approximately 160 mL of blood will be drawn at this visit.

Also at this visit, we will perform indirect calorimetry a total of 3 times (once before and twice during the insulin clamp). A transparent plastic hood will be placed over the participant's head for 30 minutes each time. A hose connects the hood to a calorimeter, which measures oxygen consumption and carbon dioxide production and calculates resting energy expenditure.

After the insulin clamp is completed, body composition will be assessed using whole body DXA. The DXA scan will be performed in the HRU to measure fat distribution, body fat, lean body mass and bone density.

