### 13. Statistical Considerations: Describe the statistical analyses that support the study design.

Group sample sizes of 15 and 15 achieve 80% power to detect a between-group difference of 0.61 in a design with 7 repeated measurements (taken at time 0, 5, 10, 30, 60, 90, 120 min) having a autoregressive AR(1)

covariance structure when the standard deviation is 1, the correlation between observations on the same subject is 0.6, and the alpha level is 0.05. To account for up to 5-10% missing data due to drop out or poor quality data, we will need to enroll a total of 32 subjects (16 per group) for this study. Data Analysis: Primary endpoints: Whole body insulin sensitivity, endogenous glucose production, whole body lipid turnover rates. Secondary endpoints: Plasma NEFA, TGs, insulin levels, metrics of body composition. Statistical Analysis: Before statistical testing, all continuous variables will be tested for normality of distribution. Summary statistics will be computed. For between-group comparisons of patient characteristics, two sample t-test or Mann-Whitney U test will be used for continuous variables, and Fisher's exact test for categorical variables. Comparisons of repeatedly measured glucose and lipid turnover rates will be made using the mixed model analysis. Fixed factors include group and time and their interactions. A random effect for subject plus an autoregressive covariance matrix will be used to accommodate within-subject correlation of repeated assessments. Linear contrasts comparing differences between groups or different time points within a group will be estimated.

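### The planned mixed model has no term for differences between women in their response to insulin; if several values per clamp phase are analysed, the standard error for a group difference in suppression is usually too small

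*Combined protocol and SAP*

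**What the plan says.** Section I, item 13 analyses the repeated glucose and lipid turnover rates with a mixed model whose fixed factors are group, time and their interaction. On covariance it says: "A random effect for subject plus an autoregressive covariance matrix will be used to accommodate within-subject correlation of repeated assessments". On estimation it says: "Linear contrasts comparing differences between groups or different time points within a group will be estimated". It names no random slope, subject-by-phase effect, unstructured covariance, robust standard error or degrees-of-freedom method. It also does not say whether the autoregressive term runs over sample order or clock time.

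The data come from Visit 3 (Section I, item 4, Hyperinsulinemic-euglycemic clamp): a 2-hour equilibration, then 2 hours at 8 mU and 2 hours at 40 mU per m² per minute. On sampling it says: "Plasma samples will be drawn at baseline and throughout the infusion period for measurement of isotope enrichment, insulin, NEFA, glycerol turnover". Times and the number of samples per phase are not given.

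The power statement uses a simpler covariance. Its claim is: "Group sample sizes of 15 and 15 achieve 80% power to detect a between-group difference of 0.61". The inputs behind that claim are seven unequally spaced samples between 0 and 120 minutes, AR(1) errors alone, SD 1, a within-woman correlation of 0.6 and alpha 0.05. It contains no variance for response to insulin.

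**The concern.** Aim 1 concerns insulin sensitivity and lipolysis. In a clamp, the informative quantity is how far insulin lowers glucose production and glycerol turnover from the fasting value. In the planned model that is a group-by-time contrast. Women differ in this response, and that difference is what the study sets out to measure.

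A random intercept removes a woman's overall level. It does not represent the fact that all her samples at 40 mU share her own degree of suppression. Averaging four such samples reduces assay and tracer noise but leaves her personal response as it was. AR(1) errors decay with lag, so they capture only part of that shared component. The model then credits the repeated samples with more information on suppression than they hold.

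At stake are the intervals and p-values for suppression of endogenous glucose production and lipid turnover, which underlie two of the three primary endpoints, with only 15 or 16 women per group.

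**Working it through.** **1. The plan's own figure.** The variance of the mean of 7 AR(1) values with correlation 0.6 and SD 1 is [7 + 2(6×0.6 + 5×0.6² + 4×0.6³ + 3×0.6⁴ + 2×0.6⁵ + 0.6⁶)]/49 = 20.71/49 = 0.4227. The SE of a group difference with 15 per group is √(2×0.4227/15) = 0.237, and 0.61/0.237 = 2.57. One-sided power is 82.2% (normal) or 80.6% (t, 28 df). Two-sided power is 72.9% or 69.9%. So the stated 80% reproduces as a one-sided test of the *time-averaged* difference. Sidedness is not stated, which is a separate matter. What matters here is that this calculation does not address suppression.

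**2. The mechanism, by hand.** All of the following inputs are assumptions:
- 11 equally spaced samples: 3 fasting, 4 at 8 mU, 4 at 40 mU.
- Total variance 1: 0.7 woman-by-phase and 0.3 AR(1) noise with correlation 0.3.
- Correlation of a woman's true fasting and 40 mU levels 0.6; 0.8 between adjacent phases.

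True variance of one woman's change (40 mU mean minus fasting mean):
- response: 2×0.7×(1−0.6) = 0.560
- noise in the mean of 4: (0.3/16)[4 + 2(3×0.3 + 2×0.09 + 0.027)] = 0.117
- noise in the mean of 3: (0.3/9)[3 + 2(2×0.3 + 0.09)] = 0.146
- total about 0.82. Of this, 0.56/0.82 = 68% does not shrink with more samples.

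The likelihood fit of random intercept + AR(1) to this covariance gives intercept variance 0.50, AR variance 0.497 and AR correlation 0.521. The intercept cancels in the change, leaving:
- mean of 4: (0.497/16)[4 + 2(3×0.521 + 2×0.271 + 0.141)] = 0.264
- mean of 3: (0.497/9)[3 + 2(2×0.521 + 0.271)] = 0.311
- covariance between the two means: −0.011
- total 0.56.

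The SE ratio is √(0.56/0.82) = 0.83. As a rough conversion, the type I error is P(|Z| > 1.96×0.83) = 10%. The same conversion gives 6% at a ratio of 0.95 and 12% at 0.80.

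**3. Simulation, 15 per group, no group difference, AR(1) by sample order.**

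| Setting (assumed) | Contrast | Model SE / true SE | Type I error |
|---|---|---|---|
| 11 samples, 70% woman-by-phase share | 40 mU minus fasting, phase means | 0.81-0.86 | 7-9.5% |
| 11 samples, 40% share | same | 0.87-0.94 | 5-9% |
| No response variation (4 samples per phase) | same | about 1.0 | 5.6% |
| 11 samples | two single time points | 0.91-0.98 | – |
| 11 samples | time-averaged group effect | 0.98-0.99 | – |
| 3 samples per phase | time-averaged group effect | about 1.0 | 5.7% |
| One rate per phase | change between phases | 0.97-0.99 | 3.9-6.4% |

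Runs per cell were 400 to 1500, so differences of a point or two are simulation noise.

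A wider grid of 36 scenarios used random-intercept SD 1, residual SD 1, response SD 0.5-1.5, residual correlation 0, 0.3 or 0.6, 3 or 4 samples per phase, and Satterthwaite degrees of freedom. Type I error was 4.7-14.3%: 16 scenarios below 7%, 17 within 7-12%, 3 above. Outside that grid, response SD 2 with phase responses correlated 0.9 gave 17.8%. Uncorrelated phase responses gave 4.0-4.6% for the 40 mU contrast.

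A two-sample t-test on one change per woman gave 3.9-6.4% in the runs of 1000-1500, which is nominal within simulation error.

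**4. AR(1) in clock time.** With phases assumed about 100 minutes apart, type I error was 5.0-7.2%. On the 0-120 minute grid printed in item 13 it was 10-20%. On that grid, however, the control without response variation was already at 6-9%, so part of the excess is misfit of the time scale. That grid also does not span the 4-hour insulin infusion.

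**The case against.** The strongest reply is that the plan does not fix the quantities that create the problem. It gives no samples per phase, no variance of response, no degrees-of-freedom method and no explicit suppression contrast. Visit 3 says blood is drawn for enrichment; it does not say that every sample becomes a separate turnover value in the model. With one rate per phase there is nothing to over-count, and the planned covariance then performs close to nominal. The contrasts item 13 does describe, between groups or between time points, are mildly affected at most if they compare single times. A random effect for subject does not strictly exclude a random response, and this is one paragraph in an application for a 32-woman study with a stated pilot goal.

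Much of this stands. A reader might infer that the plan's type I error is 7-12%, or that false positives on two primary endpoints will exceed 5%. The documents do not support either statement: 16 of the 36 scenarios lie below 7%, and the result depends on a data layout the plan leaves open. Nor can one say that clock-time AR(1) makes things worse or cures them, because the answer changes with the grid.

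What does not stand is that this is only missing detail. Item 13 names a specific covariance, and on its natural reading that covariance omits the component of variation that a clamp is designed to measure.

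**Conclusion.** The point holds in a conditional form. If several turnover values per phase enter the model, and women differ in their response to insulin, then random intercept + AR(1) by sample order usually understates the SE of a group difference in phase-averaged suppression. The understatement is about 5-20% in most scenarios, with type I error of about 5-14% instead of 5%. Both ranges rest on assumed variances, sampling times and correlations.

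The effect is confined to suppression contrasts. Contrasts between single time points are only mildly affected. The time-averaged group effect, which the power statement appears to address, keeps a correct SE. Whole-body insulin sensitivity is not named as a mixed-model outcome and is outside this point. This is a cheap improvement to the plan, not a demonstrated failure of it.

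**What to change.** In item 13, define the suppression contrast (each insulin step minus fasting), give the tracer sampling times, and choose one of these analyses:

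- Average each woman's turnover data to one value per phase (fasting, 8 mU, 40 mU) and compare groups on her change between phases with a two-sample test.
- Fit a mixed model to the three phase values with an unstructured 3×3 covariance and Kenward-Roger degrees of freedom.
- If all samples are kept, add a random woman-by-phase effect to the random subject effect.

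The first is the simplest and held its level in every setting examined. The change is to wording only; it needs no new samples, visits or participants. The price is wider intervals for suppression where response varies: 1/0.86 = 1.16 to 1/0.83 = 1.20 times as wide with a large response share, and 1/0.80 = 1.25 at the far end of the usual range. That is the width the data justify. If women hardly differ in response, almost nothing is lost.

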**SECTION II: RESEARCH INVOLVING DRUGS, BIOLOGICS, RADIOTRACERS, PLACEBOS**

*If this section (or one of its parts, A or B) is not applicable, check off N/A and delete the rest of the section.*

**A. RADIOTRACERS**

N/A

**B. DRUGS/BIOLOGICS**

S [2H5]-Glycerol and [6,6-2H]- Glucose to be used during the clamp procedure. A primed-continuous infusion of regular insulin will be given at 8 mU/(m^2 × min) during the first 2 hours, and increased to 40 mU/(m^2 × min) for the subsequent 2 hours.

**C. Use of Placebo:**  Not applicable to this research project

**1. Continuation of Drug Therapy After Study Closure**  Not applicable to this project

1. Identify whether FDA approval has been granted and for what indication(s). – N/A

2. All protocols which utilize a drug, biologic or radiotracer not approved by, but regulated by, the FDA, or a radiotracer regulated by the RDRC, must provide the following information: N/A

a. What is the Investigational New Drug (IND) number assigned by the FDA?

b. Who holds the IND?

c. All protocols which utilize a radiotracer not approved by, but regulated by the FDA must provide the IND number:

Alternatively, use of the investigational radiotracer may be under RDRC/RSC oversight: (check if appropriate)

Alternatively, an exemption from IND filing requirements may be sought for a clinical investigation of a drug product that is lawfully marketed in the United States.

Exempt Category 1

The clinical investigation of a drug product that is lawfully marketed in the United States can be exempt from IND regulations if all of the following are yes:

- i. The intention of the investigation is NOT to report to the FDA as a well-controlled study in support of a new indication for use or to be used to support any other significant change in the labeling for

the drug.  Yes  No

ii. The drug that is undergoing investigation is lawfully marketed as a prescription drug product, and the intention of the investigation is NOT to support a significant change in the advertising for the product.  Yes  No

iii. The investigation does NOT involve a route of administration or dosage level or use in populations or other factor that significantly increases the risks (or decreases the acceptability of the risks) associated with the use of the drug product.  Yes  No

iv. The investigation will be conducted in compliance with the requirements for institutional (HIC) review and with the requirements for informed consent of the FDA regulations (21 CFR Part 50 and 21 CFR Part 56).  Yes  No

v. The investigation will be conducted in compliance with the requirements regarding promotion and charging for investigational drugs.  Yes  No

2. Background Information: Provide a description of previous human use, known risks, and data addressing dosage(s), interval(s), route(s) of administration, and any other factors that might influence risks. If this is the first time this drug is being administered to humans, include relevant data on animal models.

[2H5]-Glycerol and [6,6-2H]- Glucose to be used during the clamp procedure. A primed-continuous infusion of regular insulin will also be given at 8 mU/(m^2 × min) during the first 2 hours, and increased to 40 mU/(m^2 × min) for the subsequent 2 hours.

Hyperinsulinemic-euglycemic clamp: The infusion of insulin and glucose poses a small risk that plasma glucose will fall below the predetermined level (90-100 mg/dl) resulting in hypoglycemia, which can be quickly reversed with IV dextrose infusion. To avoid hypoglycemia during the clamp, plasma glucose will be checked every five minutes using a bedside glucose monitor. Based on these measurements, the plasma glucose will be adjusted via the dextrose infusion. The risks of drawing blood and inserting an IV line are detailed above. The studies will be performed under the supervision of a qualified physician or nurse practitioner. All solutions that are administered via IV will be sterile, pyrogen free, and prepared in a sterile environment. During glucose infusion, dextrose 20 (20% glucose) will be used to decrease the risk of thrombophlebitis that is associated with hypertonic glucose solutions (50% glucose).

6,6D2-glucose and D5-glycerol: The infusion of 6,6D2-glucose and D5-glycerol involves no radioactivity, and the glucose and glycerol are metabolized just as the unlabeled metabolites. Clinical research studies using these tracers have been used at Yale for decades with no adverse effects. The isotopes are purchased from (Cambridge Isotopes, Inc.) in powder form which has been certified to be sterile and free of pyrogens. They are made into a solution by the YNHH IDS. The solutions are tested to be free of pyrogens and to be sterile before being administered to the participants. All certifications are kept with the IDS.

3. Source: a) Identify the source of the drug or biologic to be used. – information noted above

b) Is the drug provided free of charge to subjects?  Yes  No

If yes, by whom? The drug will be provided through funding received by the Principal Investigator, [name] [name] for the conduction of this study.

4. Storage, Preparation and Use: Describe the method of storage, preparation, stability information, and for

parenteral products, method of sterilization and method of testing sterility and pyrogenicity.

Check applicable Investigational Drug Service utilized:

YNHH IDS

Yale Cancer Center

CMHC Pharmacy

West Haven VA

PET Center

None

Other:

D.DEVICES

N/A

### SECTION III: RECRUITMENT/CONSENT AND ASSENT PROCEDURES

#### 1. Targeted Enrollment:

- Targeted for enrollment at Yale for this protocol: 32
- If this is a multi-site study, give the total number of subjects targeted across all sites: N/A

#### 2. Indicate recruitment methods below. Attach copies of any recruitment materials that will be used.

 Flyers	 Internet/web postings	 Radio
 Posters	 Mass email solicitation	 Telephone
 Letter	 Departmental/Center website	 Television
 Medical record review*	 Departmental/Center research boards	 Newspaper
 Departmental/Center newsletters	 Web-based clinical trial registries	 Clinicaltrials.gov
 YCCI Recruitment database	 Social Media (Twitter/Facebook):	
 Other:		

\* Requests for medical records should be made through JDAT as described at

<http://medicine.yale.edu/ycci/oncore/availableservices/datarequests/datarequests.aspx>

**3. Recruitment Procedures:**

- Describe how potential subjects will be identified.

Potential subjects will be identified as indicated below using the methods identified in #2 above:

- Self-Identify
- Provider Referrals
- Study Team Members
- Existing registries, studies, and websites where participants have previously provided informed consent or a request to be contacted for research utilizing their preferred method of contact when known.
- Joint Data Analytics Team (JDAT)
- Potential subjects may be identified by MFM clinical providers/staff and/or research staff during routine clinical care at the Maternal Fetal Medicine Center at [name].

How these options will be utilized is further described in section "b" below.

- Describe how potential subjects are contacted.

- Self-Identify and Provider Referrals: Participants will self-identify using IRB approved recruitment materials that will be posted locally. Recruitment materials will display the contact information of the study team in addition to a description of the study. Potential participants may also be approached by their medical provider. Additionally, participants may be approached by study personnel at community events, or at various locations where potentially eligible patients are seen when facilitated through the participant's treatment team, including at Yale SOM, YNHH, YMG, and VA Connecticut Healthcare System.
  - Potential subjects may be approached in person, at the time of routine clinical care in MFM clinic. If time does not allow (either a research team member is not available to speak with the potential subject or the potential subject does not have time to discuss the study), potential subjects may be called after their clinical visit to discuss the study. In this situation, the potential subject would be provided with a brochure about the study during their clinic visit and will be told that a research team member may be calling them about a study they are potentially eligible for. The person contacting the potential subject will be a research team member who may be known to the subject or may be calling on behalf of the PI.
- Recruitment through Existing Registries and Studies: Participants will be recruited through the YCCI website/registry/Help Us Discover and ClinicalTrials.gov website. Participants may also be identified through their participation in the Yale University Reproductive Sciences Longitudinal Pregnancy study. Study personnel will use MyChart, traditional mail, telephone or email of patients recruited through this method. If the EPIC registration module provides a preferred method of contact, that method will be utilized. If the participant is not registered in EPIC but has expressed interest in a research study by calling, emailing, filling out an online questionnaire, or speaking with study personnel face-to-face, the patient will be contacted by their means of preference, if stated.
- Recruitment through JDAT: The Joint Data Analytics Team (JDAT) will also be used to query eligible patients in EPIC based on the eligibility criteria outlined above (#8). JDAT will identify and send a study communication to potential participants based on these criterion that fall within the following time period: the last 18 months. Potential participants who do not use MyChart will receive a paper mailing including information about the study. JDAT will not identify the potential participants to the researchers, and therefore the researchers will receive no identifiable information from JDAT.
- Messaging to Study Participants:  
The following wording will be used in the letter or MyChart message patients receive via JDAT describing the study and inviting them to participate:
  - "You are receiving this notification because you may qualify and be interested in a study looking at the effect of breastfeeding on blood sugar, insulin and fat in women with a history of

gestational diabetes. The Yale New Haven Health electronic health record system has searched medical conditions to find people who may be good matches for research studies. No one has looked at your record and no information has been shared with any research doctor or research team member. Just because you received this message does not mean that you are in a research study or that you have to decide to be in this or any study.

You may be interested and eligible to participate in a research study conducted by Yale University investigators to better understand breastfeeding and diabetes.

